# 9.5.2. Statistical consideration for analysis (Amended 26 May 2022)

Not applicable.

# 10. SUPPORTING DOCUMENTATION AND OPERATIONAL CONSIDERATIONS

# 10.1. Appendix 1: Regulatory, Ethical, and Study Oversight Considerations

# 10.1.1. Regulatory and ethical considerations

- This study will be conducted in accordance with the protocol and with:
  - Consensus ethical principles derived from international guidelines including the Declaration of Helsinki and Council for International Organisations of Medical Sciences (CIOMS) International Ethical Guidelines
  - Applicable ICH Good Clinical Practice (GCP) Guidelines
  - Applicable laws and regulations
- The protocol, protocol amendments, ICF or Informed Assent Form, Investigator Brochure, and other relevant documents (e.g. advertisements) must be submitted, to an IRB/IEC by the investigator for review and approval. These documents will be signed and dated by the investigator before the study is initiated.
- Any protocol amendments will require IEC/IRB approval before implementation of changes made to the study design, except for changes necessary to eliminate an immediate hazard to study participants.
- GSK will provide full details of the above procedures to the investigator, either verbally, in writing, or both.
- The investigator will be responsible for the following:
  - Providing written summaries of the status of the study to the IRB/IEC annually or more frequently in accordance with the requirements, policies, and procedures established by the IRB/EC.
  - Notifying the IRB/IEC of SAE(s) or other significant safety findings as required by IRB/IEC procedures.
  - Providing oversight of the conduct of the study at the site and adherence to requirements of 21 CFR, ICH guidelines, the IRB/IEC, European regulation 536/2014 for clinical studies (if applicable), and all other applicable local regulations.

# 10.1.2. Financial disclosure

Investigators and sub-investigators must provide the sponsor with full and accurate financial disclosure, as requested, to allow the sponsor to submit complete and accurate financial certification or disclosure statements to the appropriate regulatory authorities. Investigators must provide their financial interest information before initiation of the study center and again at the end of the study. Investigators are responsible for providing

a financial disclosure update if their financial interests change at any point during study participation and for 1 year after completion of the study.

# 10.1.3. Informed consent process

The investigator or his/her representative must fully explain the nature of the study to the participant and answer all questions regarding the study.

Participants must be informed that their participation is voluntary.

Freely given and written/witnessed/thumb printed informed consent must be obtained from each participant as appropriate, prior to participation in the study.

The content of the informed consent form must meet the requirements of 21 CFR 50, local regulations, ICH guidelines, Health Insurance Portability and Accountability Act (HIPAA) requirements, where applicable, and the IRB/IEC or study center.

The medical record must include a statement that written, or witnessed/thumb printed informed consent was obtained before the participant was enrolled in the study and the date the consent was obtained. The authorized person obtaining the informed consent must also sign the ICF.

Participants must be re-consented to the most current version of the ICF(s) or an ICF addendum during their participation in the study.

A copy of the ICF(s) must be provided to the participants.

# 10.1.4. Data protection

Participants will be assigned a unique identifier by the sponsor. Any participant records or datasets transferred to the sponsor will contain only the identifier. Name and any other information which would identify the participant will not be transferred.

The participants must be informed that:

- Her personal study-related data will be used by the sponsor in accordance with local data protection law.
- Her medical records may be examined by Clinical Quality Assurance auditors or other authorized personnel appointed by the sponsor, by appropriate IRB/IEC members, and by inspectors from regulatory authorities.
- GSK will ensure protection of the personal data of the investigator and site staff which is collected within the framework of and for the purpose of the study, in accordance with the Data Privacy Notice that will be sent to the site staff.

The participants must be notified about their rights regarding the use of their personal data in accordance with the data privacy section of the ICF.

### 10.1.5. Committees structure

Safety oversight will be provided by a safety review team (SRT) composed of GSK RSV team members.

# 10.1.6. Dissemination of clinical study data

The key design elements of this protocol and results summaries will be posted on www.ClinicalTrials.gov and/or GSK Clinical Study Register in compliance with applicable regulations/GSK policy. GSK will aim to register protocols summaries prior to study start and target results summaries submission within 12 months of primary/ study completion date. Where external regulations require earlier disclosure, GSK will follow those timelines.

Where required by regulation, summaries will also be posted on applicable national or regional clinical trial registers.

Where required by applicable regulatory requirements, an investigator signatory will be identified for the approval of the study report, and provided reasonable access to statistical tables, figures, and relevant reports. GSK will also provide the investigator with the full summary of the study results. The investigator is encouraged to share the summary results with the study participants, as appropriate.

GSK will provide the investigator with the randomization codes for their site only after completion of the full statistical analysis.

GSK intends to make anonymized patient-level data from this trial available to external researchers for scientific analyses or to conduct further research that can help advance medical science or improve patient care. This helps ensure the data provided by trial participants are used to maximum effect in the creation of knowledge and understanding.

# 10.1.7. Data quality assurance

The investigator should maintain a record of the location(s) of their respective essential documents, including source documents. The document storage system used during the trial and for archiving (irrespective of the type of media used) should provide for document identification, version history, search, and retrieval.

Essential trial documents may be added or removed where justified (in advance of trial initiation) based on their importance and relevance to the trial. When a copy is used to replace an original document (e.g. source documents, CRF), the copy should fulfill the requirements for certified copies.

All participant data related to the study will be recorded on printed or electronic CRF unless transmitted to the sponsor or designee electronically (e.g. laboratory data). The investigator is responsible for verifying that data entries are accurate and correct by physically or electronically signing the eCRF.

The investigator must maintain adequate and accurate source documents and trial records that include all pertinent observations on each of the site's trial participants that supports information entered in the eCRF.

The investigator must permit study-related monitoring, audits, IRB/IEC review, and regulatory agency inspections and provide direct access to source documents or certified copies for such review and inspection.

The sponsor or designee is responsible for the data management of this study including quality checking of the source data.

Study monitors will perform ongoing source data verification to confirm that data entered in the eCRF by authorized site personnel are attributable, legible, contemporaneous, original, accurate, and complete. Changes to source data must be traceable, not obscure the original entry, and be fully explained if necessary (e.g. via an audit trail). The safety and rights of participants must be protected, and the study conducted in accordance with the currently approved protocol and any other study agreements, ICH GCP, and all applicable regulatory requirements.

Quality tolerance limits (QTLs) will be pre-defined in the Study Management Plan to identify systematic issues that can impact participant safety and/or the reliability of study results. These pre-defined parameters will be monitored during the study. Important deviations from the QTLs and remedial actions taken will be summarized in the CSR.

Trial records and source documents pertaining to the conduct of this study, including signed ICFs, must be retained by the investigator for 25 years from issuance of the final CSR/equivalent summary unless local regulations or institutional policies require a longer retention period. No records may be destroyed during the retention period without the written approval of the sponsor. No records may be transferred to another location or party without written notification to the sponsor.

# 10.1.8. Source documents

Source documents provide evidence to establish the existence of the participant and substantiate the integrity of collected data. The investigator should maintain a record of the location(s) of their source documents.

Data transcribed into the eCRF from source documents must be consistent with those source documents; any discrepancies must be explained. The investigator may need to request previous medical records or transfer records, depending on the study. Also, current medical records must be available.

Definitions of what constitutes source data and documents can be found in the Glossary of terms.

# 10.1.9. Study and site start and closure

GSK or its designee reserves the right to close the study site or terminate the study at any time for any reason at its sole discretion, provided there is sufficient notice given to account for all participants safe exit from study.

Regular closure of study sites will occur upon study completion. A study site is considered closed when all required data/documents and study supplies have been collected and a study site closure visit has been performed.

The investigator may initiate study site closure at any time, provided there is reasonable cause and enough notice in advance of the intended termination.

Reasons for the early closure of a study site by the sponsor or investigator may include but are not limited to:

- Failure of the investigator to comply with the protocol, the requirements of the IRB/IEC or local health authorities, the sponsor's procedures, or GCP guidelines
- Inadequate recruitment of participants by the investigator
- Discontinuation of further study intervention development

# 10.1.10. Publication policy

GSK aims to submit the results of the study for publication in searchable, peer reviewed scientific literature within 18 months from the Last Subject Last Visit (LSLV) for interventional studies and follows the guidance from the International Committee of Medical Journal Editors (ICMJE).

# 10.2. Appendix 2: Clinical laboratory tests (Amended 26 May 2022)

# **10.2.1. Protocol required safety laboratory assessments**

Assay descriptions could be subject to change, due to assay re-development and/or qualification.

### RSV-A and RSV-B neutralization assays

The RSV-A and RSV-B neutralization assays are functional assays that measure the ability of serum antibodies to neutralize RSV entry and replication in a host cell line.

Virus neutralization is performed by incubating a fixed amount of RSV with serial dilutions of the test serum. Then, the serum-virus mixture is transferred onto a Vero cells culture and incubated for two days to allow infection of Vero cells. Thereafter, RSV-infected cells are detected by the visualization of the number of plaques.

### RSVPreF3 IgG ELISA

The ELISA assay is based on an indirect ELISA allowing the detection and the quantification of specific IgG antibodies directed against RSVPreF3 in human serum samples and related to reference standard. The optical density of each sample dilution is then interpolated on the reference standard. The corresponding antibody concentration, corrected for the dilution factor, is expressed in arbitrary ELISA Laboratory Units per milliliter (ELU/mL).

### FLU Hemagglutination-inhibition (HI) assay

Hemagglutination inhibition (HI) antibody titres are determined using the method derived from the WHO Manual on Animal Influenza Diagnosis and Surveillance, WHO/CDS/CSR/NCS/2002.5.

Measurements are conducted on thawed frozen serum samples with a standardized and comprehensively validated micro-method. Briefly, serum samples are treated with receptor destroying enzyme (RDE) overnight, diluted to 1:10, and serial diluted 2- fold in triplicate from 1:10 to 1:10240. After addition of an equal volume of standardized virus (4 HA / 25  $\mu$ L), neutralization is performed for 1 hour at room temperature, followed by addition of the RBCs. After 30 minutes, plates are tilted and the titer is the reciprocal of the last dilution that fully inhibits hemagglutination as compared to a RBC control well. Each sera sample will be tested in triplicate within the same assay. The three titer results will be reported as will the geometric mean titer (GMT) for the triplicate.

The tests detailed in Table 20 will be performed by the local laboratory.

All clinical and safety laboratory tests will be performed by local laboratory(ies). All assessments of immune response will be performed centrally (by GSK or by a GSK designated laboratory).

Protocol-specific requirements for inclusion or exclusion of participants are detailed in Section 6 of the protocol.

The investigator is not allowed to do extra testing on samples outside of what has been agreed upon by the ethics committees.

### Table 20 Protocol required safety laboratory assessments

System	Discipline	Component	Method	Scale	Laboratory
Urine 		Pregnancy	As per local practice; dipstick provided by GSK Biologicals	Ordinal	At investigator's laboratory

The tests detailed in Table 20 will be performed by the local laboratory.

# 10.3. Appendix 3: Adverse Events: definitions and procedures for recording, evaluating, follow-up, and reporting Definition of AE

# 10.3.1. Definition of an AE

An AE is any untoward medical occurrence (an unfavorable/unintended sign - including an abnormal laboratory finding), symptom, or disease (new or exacerbated) in a clinical study participant that is temporally associated with the study intervention. The AE may or may not be considered related to the study intervention.

# 10.3.1.1. Events Meeting the AE Definition

- Significant or unexpected worsening or exacerbation of the condition/indication under study.
- Exacerbation of a chronic or intermittent pre-existing condition including either an increase in frequency and/or intensity of the condition.
- New conditions detected or diagnosed after administration of the study intervention even though they may have been present before study start.
- Signs, symptoms, or the clinical sequelae of a suspected drug, disease or other interaction.
- Signs, symptoms, or the clinical sequelae of a suspected overdose of either the study intervention or a concurrent medication.
- Signs or symptoms temporally associated with administration of the study intervention.

- Signs, symptoms that require medical attention (e.g. hospital stays, physician visits and emergency room visits).
- Significant failure of an expected pharmacologic or biological action.
- Pre- or post- intervention events that occur as a result of protocol-mandated procedures (i.e. invasive procedures, modification of participant's previous therapeutic regimen).
- Clinically significant abnormal laboratory findings or other abnormal assessments that are present at baseline and significantly worsen following the start of the study will also be reported as AEs or SAEs.
- AEs to be recorded as solicited AEs are described in the Section 10.3.3. All other AEs will be recorded as UNSOLICITED AEs.
- The signs, symptoms, and/or clinical sequelae resulting from lack of efficacy will be reported as AE or SAE if they fulfill the definition of an AE or SAE.

### 10.3.1.2. Events NOT Meeting the AE Definition

- Situations where an untoward medical occurrence did not occur (e.g. social and/or convenience admission to a hospital, admission for routine examination).
- Anticipated day-to-day fluctuations of pre-existing disease(s) or condition(s) present or detected at the start of the study that do not worsen.
- Pre-existing conditions or signs and/or symptoms present in a participant before the study intervention. These events will be recorded in the medical history section of the eCRF.
- Hospitalization for elective treatment of a pre-existing condition (known or diagnosed before signing the informed consent) that did not worsen from baseline.
- Any clinically significant abnormal laboratory findings or other abnormal safety assessments associated with the underlying disease, unless judged by the investigator to be more severe than expected for the participant's condition.
- Disease-related events (DRE), typically associated with the disease under study. These events will be recorded in the participant's eCRF and will be monitored by the SRT on a routine basis. However, if 1 or both of the following conditions apply, then the event should be reported promptly to GSK as an SAE (see Section 10.3.8):
  - The event is, in the investigator's opinion, of greater intensity, frequency, or duration than expected for the individual participant, or
  - The investigator considers that there is a reasonable possibility that the event was related to the administration of the study intervention

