### 10.3.2. Definition of an SAE

### An SAE is any untoward medical occurrence that:

### a. Results in death.

b. Is life-threatening

Note: The term 'life-threatening' in the definition of 'serious' refers to an event in which the participant was at risk of death at the time of the event. It does not refer to an event, which hypothetically might have caused death, had it been more severe.

c. Requires hospitalization or prolongation of existing hospitalization

Note: In general, hospitalization signifies that the participant has been admitted at the hospital or emergency ward for observation and/or treatment that would not have been appropriate in the physician's office or in an out-patient setting. Complications that occur during hospitalization are also considered AEs. The event will also be considered serious if a complication prolongs hospitalization or fulfills any other serious criteria. When in doubt as to whether 'hospitalization' occurred or was necessary, the AE should be considered serious.

d. Results in disability/incapacity

Note: The term disability means a substantial disruption of a person's ability to conduct normal life functions. This definition is not intended to include experiences of relatively minor medical significance such as uncomplicated headache, nausea, vomiting, diarrhea, influenza like illness, and accidental trauma (e.g. sprained ankle) which may interfere or prevent everyday life functions but do not constitute a substantial disruption.

- e. Is a congenital anomaly/birth defect in the offspring of a study participant.
- f. Abnormal pregnancy outcomes (e.g. spontaneous abortion, fetal death, stillbirth, congenital anomalies, ectopic pregnancy).
- g. Other situations

Medical or scientific judgment must be exercised in deciding whether reporting is appropriate in other situations. Important medical events that may not be immediately life-threatening or result in death or hospitalization but may jeopardize the participant or require medical or surgical intervention to prevent one of the other outcomes listed in the above definition should be considered serious. Examples of such events are invasive or malignant cancers; intensive treatment in an emergency room or at home for allergic bronchospasm; blood dyscrasias; and convulsions that do not result in hospitalization.

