## **4.2. Primary Endpoint(s) Analyses**

### **4.2.1. Safety analysis**

The analysis of solicited administration site event (associated with RSV or Flu) and solicited systemic event will be performed on solicited safety set.

- The number and percentage with exact 95% CI of participants reporting each solicited administration site event (any grade, each grade) and solicited systemic event (any, each grade) during the 7-day follow-up period after dosing will be tabulated by maximum intensity per participant for each study group.
- For fever during the 7-day follow-up period after vaccination, the number and percentage of participants reporting any fever (i.e., temperature  $\geq 38$  °C) and fever by half degree (°C) cumulative increments, any Grade 3 fevers, will be reported.
- Duration in days of solicited administration site and systemic events within 7 days after vaccination will be tabulated by study group and overall. The derivation rule of duration in days for solicited events is detailed in section [6.2.4.9](#).

The analysis of unsolicited AEs and SAEs will be performed on ES.

- The number and percentage of participants reporting unsolicited AEs within 30 days after dosing with exact 95% CIs will be tabulated by group and by Medical Dictionary for Regulatory Activities (MedDRA) terms.
- Similar tabulations will be done for Grade 3 unsolicited AEs, for any causally related unsolicited AEs, and for Grade 3 related unsolicited AEs.
- The number and percentage of participants reporting at least one SAE within 30 days after dosing with exact 95% CIs will be tabulated by group and by MedDRA terms.
- The number and percentage of participants reporting at least one SAE up to study end with exact 95% CIs will be tabulated by group and by MedDRA terms.
- By-participant listings of SAEs, and AEs leading to study withdrawal will be prepared.

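### The disease-related-event clause in Protocol 10.3.1.2 contradicts the AE and SAE definitions and, followed literally, can miscount the descriptive primary safety endpoints

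*Protocol*

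**What the plan says.** Protocol 10.3.1.2 sets out what does not meet the AE definition. Its last bullet is "Disease-related events (DRE), typically associated with the disease under study". On their handling it says: "These events will be recorded in the participant's eCRF and will be monitored by the SRT on a routine basis". It then adds that "if 1 or both of the following conditions apply, then the event should be reported promptly to GSK as an SAE". The first condition is that the investigator thinks the event "of greater intensity, frequency, or duration than expected for the individual participant"; the second is a reasonable possibility of a causal link to the study intervention.

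Four other parts of the same appendix bear on these illnesses:

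- 10.3.1 counts a new disease arising in temporal association with the intervention as an AE.
- 10.3.1.1 counts newly diagnosed conditions as AEs. It also says that the consequences "resulting from lack of efficacy will be reported as AE or SAE if they fulfill the definition of an AE or SAE".
- 10.3.2 applies its seriousness criteria to untoward medical events of any kind. One criterion is "Requires hospitalization or prolongation of existing hospitalization". There is no exemption for disease-related events.
- 10.3.9.1 warns against confusing intensity with seriousness and ties seriousness to the outcomes in 10.3.2.

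The current SAP (Amendment 2), Section 4.2.1, tabulates "The number and percentage of participants reporting unsolicited AEs within 30 days after dosing with exact 95% CIs", and SAEs to Day 30 and to study end. All three are primary safety endpoints in Protocol Table 3.

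**The concern.** Disease-related-event wording belongs in trials of patients who already have a disease with a known course. Here the participants are healthy women aged 18-49, so neither the disease under study nor an expected course has an obvious meaning. RSV illness is the natural candidate, because RSV is the target of the investigational vaccine.

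A site that follows the clause can err in two directions. It can file a non-serious RSV illness as a disease-related event, which the SAP puts in no table. It can also send in a non-serious illness as an SAE because it seemed more intense than expected or possibly related. Both decisions rest on investigator judgement, and in the co-administration comparison only the participant is blinded (6.3.5).

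At stake are the unsolicited AE and SAE percentages. Amendment 3 made SAEs to study end a primary endpoint, and the same amendment reports safety signals in the RSV MAT-009 study, so the meaning of an SAE in these tables should be beyond argument.

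**Working it through.** **Comparing the rules**

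| Case | 10.3.1.2 clause | Rest of the appendix |
|---|---|---|
| Non-serious RSV illness, expected course, judged unrelated | Not an AE | An AE under 10.3.1 and 10.3.1.1 |
| Non-serious illness, more intense than expected or possibly related | Reported as an SAE | An AE only: no 10.3.2 criterion met, and 10.3.9.1 separates intensity from seriousness |
| Hospitalised illness, expected course, judged unrelated | Not an AE, and neither SAE trigger met | An SAE under 10.3.2 |

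The lack-of-efficacy sentence in 10.3.1.1 does not settle the first row. It applies only to events that already fulfil the definition, and that is the question 10.3.1.2 answers in the negative. In the second row, relatedness cannot have been meant to imply seriousness, since SAP 4.2.1 plans separate tables of causally related unsolicited AEs.

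**Looking for a rule that resolves the conflict**

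The clause refers the reader to 10.3.8, which has no rule for these events. The Schedule of Activities and Table 11 have no row for them. The SAP has neither an output nor a counting rule. Protocol 8.3.5 shows the consistent alternative: COVID-19 cases go through the ordinary AE and SAE criteria.

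**The plan's own safety figures (Protocol 9.2.4 and Table 18)**

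- Probability of at least one event, n = 440, true rate 1%: 1 - 0.99^440 = 0.988, as stated (98.8%).
- Exact upper 95% limit for zero events, 1 - 0.025^(1/n): 0.56% for n = 660 and 0.83% for n = 440, as stated. The other six rows of Table 18 also reproduce.

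**Illustration 1: events set aside**

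Assumptions: a true event rate of 1%, borrowed from 9.2.4, and a share f of events filed as disease-related. The documents give neither for RSV or influenza illness. With n = 440, P(at least one counted) = 1 - (1 - 0.01(1 - f))^440.

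| f | 0 | 10% | 25% | 50% | 75% | 100% |
|---|---|---|---|---|---|---|
| Probability | 98.8% | 98.1% | 96.4% | 89.0% | 66.8% | 0% |

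**Illustration 2: non-serious events escalated**

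Start from no true SAE in a group of 440 and report k non-serious illnesses as SAEs. The percentage is k/440, with an exact 95% CI.

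| k | Percentage | 95% CI |
|---|---|---|
| 0 | 0% | 0-0.83 |
| 1 | 0.23% | 0.01-1.26 |
| 3 | 0.68% | 0.14-1.98 |
| 5 | 1.14% | 0.37-2.63 |

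In the pooled RSV-alone group one such event adds 1/660 = 0.15 percentage points.

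**Timing**

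Protocol 2.3 dates the stop of vaccination in the non-pregnant studies to 1 March 2022, and Amendment 3 is dated 26 May 2022. That is 30 + 30 + 26 = 86 days later, so Day 1-30 collection was over. Day 181 after a vaccination on 1 March falls on 28 August 2022, so some SAE follow-up may still have been open.

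**The case against.** The strongest reply is that the clause is inert template text. No disease-related event is named and no collection row exists, so sites may never have used it. Ordinary illness is well covered elsewhere: new disease, medically attended symptoms and events that worry the participant are all collected as AEs, and 10.3.2(d) mentions influenza-like illness when applying normal seriousness criteria. Escalated events do have a timeframe, since Table 12 gives 24 hours for SAEs. Events filed under the clause stay in the eCRF and can be recovered. The safety endpoints are descriptive, with no test or decision rule attached. All of this stands and limits the consequence. It does not tell a site which of two opposed rules to follow, nor the statistician how to count an event filed under the clause.

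A reader might also draw three stronger inferences that the documents do not support:

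- That hospitalised RSV or influenza cases drop out of the SAE counts. Section 10.3.2 does not require an event to be an AE first and exempts nothing, so such a case is an SAE on its face.
- That influenza cases are removed unequally, because the RSV-alone groups have no influenza vaccine until Day 31. This needs influenza to be the disease under study, a term the protocol leaves undefined; Flu D-QIV is the co-administered product.
- That an AE rate of 5.0% (33/660, 95% CI 3.47-6.95) could become 0% (upper limit 0.56%). This borrows a row of Table 18 that illustrates any AE, and assumes that every event is such an illness and that every one is diverted.

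**Conclusion.** The clause should not stay. It contradicts 10.3.1, 10.3.1.1, 10.3.2 and 10.3.9.1, and neither 10.3.8 nor the SAP resolves the conflict. Two miscounts can follow from it as written: a non-serious RSV illness missing from the Day 1-30 unsolicited AE tables, and a non-serious illness in the SAE tables without a 10.3.2 criterion. For hospitalised cases the defect is a contradiction, not a demonstrated loss.

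The size is unknown. It depends on how many illnesses occurred, how many sites used the clause, and whether influenza was read into it; the documents give none of these. The tables under the working show scale under stated assumptions and are not estimates. The immunogenicity tests, sample size and alpha are untouched. The point is worth acting on because the affected endpoints are primary and the correction is cheap.

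**What to change.** 1. In Protocol 10.3.1.2, delete the disease-related-event bullet with its two conditions, and delete DRE from the abbreviation list. State that RSV, influenza and other respiratory illnesses are classified by 10.3.1 and 10.3.2, as 8.3.5 already does for COVID-19. At this stage the deletion can affect only remaining SAE follow-up.
2. Before database freeze, query sites for any event recorded as disease-related, and identify any SAE reported solely through the two triggers. Reclassify each by 10.3.1 and 10.3.2, before unblinding where possible.
3. Add a sentence to SAP 4.2.1 saying that events so reclassified are counted in the unsolicited AE and SAE tables according to their corrected status. If the query finds none, say so in the study report.

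The cost is a wording change, one data query and one SAP sentence. AE percentages may rise slightly. Step 2 matters most, because collection was largely complete at Amendment 3.
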